Effect of Flumazenil on Hypoactive Delirium in the ICU: A Double-Blind, Placebo-Controlled Pilot Study

NCT: 02899156

Document Date: September 25, 2017

Document Type: Study Protocol with Statistical Analysis

Objectives

The primary objectives was to determine the effect of flumazenil on delirium-free days for critically ill patients with benzodiazepine-associated hypoactive delirium. Delirium free days were defined as the number of days in the first 14 days during which the patient was alive without delirium or coma from any cause

The primary safety objective was the occurrence of severe refractory agitation, which was defined as RASS of +2 to +4 that did not resolve by decreasing the infusion rate of study drug.

Secondary outcomes included probability of delirium resolution, ICU LOS, maximum rate and duration of study infusion, rescue sedative use, and mechanical ventilator-free days.

The hypothesis was that flumazenil continuous infusion may decrease duration of delirium by reversing benzodiazepine-associated hypoactive delirium.

Study Design

This was a single-center randomized, double-blind, placebo-controlled study. Critically ill adult patients with suspected BZD-associated hypoactive delirium may be eligible.

Upon completion of screening and determining eligibility, patients received a test dose of flumazenil. If response was noted (defined as a change in RASS of +1 to +2), patients were randomized to receive standard of care and placebo infusion or standard of care and flumazenil infusion.

Methods

The PI or a co-investigator screened for subjects for inclusion via a daily drug utilization report of benzodiazepine use in the Intensive Care Units. Upon pre-qualification via EMR screening, the investigator performed an in-person assessment to confirm inclusion criteria have been met and patients do not meet exclusion criteria.

Screening included:

- review of the subjects current and prior to admission medication list (via medication reconciliation performed by PI/pharmacy medication reconciliation team, or urine drug toxicity screen)
- review of past medical history (history of seizure, TBI, etc.) to identify exclusion criteria
- review of available urine drug toxicity screen to identify ingestion of pro-convulsant or home benzodiazepine medication. If there was no available urine drug toxicity screen and the patient was greater than 72 hrs from admission there was no requirement for ordering one unless there was a high suspicion for recreational drug use prior to admission
- review of available pregnancy test in females aged 18 -55 y.o. If pregnancy testing was not already performed, the PI discussed ordering a pregnancy test with the primary ICU attending prior to enrollment. If the pregnancy test was positive, the subject was not enrolled.

- all patients who were screened will be tabulated in order to document reasons for exclusion. PHI was not retained for this process.
- confirmed documentation of **RASS -3 to 0 and CAM-ICU positive**
- the study was then discussed with the primary attending physician caring for the patient and permission was obtained to approach patient and/or LAR to obtain consent. At that time the patient's home medication list was confirmed with the LAR to identify any history of taking pro-convulsants.

Test dose administration and monitoring (ICU-only):

- after consent was obtained enrollment into the trial occurred, subjects received a test dose of flumazenil 0.1-0.5 mg as IV push over 15 seconds administered by the bedside nurse. May repeat every 5-10 minutes up to a MAX of 2 mg total (assess for up to 60 minutes after last dose) (onset of 0.6 mg dose in healthy volunteers was 5 minutes).
- for all patients meeting inclusion criteria and for whom consent had been obtained the PI entered each subject's test dose response (positive/negative) on a study log
- subjects' response was assessed by the PI, bedside nurse and a member of the primary care team who remained at bedside for 30 minutes after the last test was administered
- a copy of the EKG was performed 10 minutes and 60 minutes after the first dose and was scanned into the subject's profile
- if response (defined as a change in RASS of +1 to +2) was noted, then randomization to standard of care and flumazenil or standard of care and placebo occurred
- responders had a sign posted on his/her door to indicate that the patient was part of a study
- patients that did not respond to test dose were not randomized
- to ensure proper safety monitoring, the PI, a member of the primary care, and the bedside nurse (administering) were present to monitor for any complications for 30 minutes after the last test dose.

Infusion titration post-randomization (ICU-only):

1. Responders to flumazenil:
 - standard of care + flumazenil 2.5 mg/50 mLs 0.9% NaCl, or 5% dextrose (0.05 mg/mL) IV continuous infusion
 - Dosing range: 0.025 mg/hr – 0.3 mg/hr (0.5 -6 ml/hr)
 - Start at @ 2 mLs per hour (0.1 mg/hr., 2.4 mg/24 hours)
 - Titration by 1 mL (0.05 mg) or as clinically indicated per study investigator every 60 minutes for target RASS (0 to +1)
**Patient care order placed for nurse to monitor RASS every 1 hour (standard of care is every 2 hrs.).
 - Maximum Rate: 6 mLs/hr. (0.3 mg/hr.)
 - If RASS +2 to +3, decrease dose by 0.05mg (1 mL) or as clinically indicated per study investigator every 60 minutes or HOLD if at the lowest rate of 0.025 mg/hr (0.5ml/hr) and re-assess in 1 hour.
 - If RASS +4, HOLD regardless of rate and re-assess in 1 hour.
 - standard of care + placebo (50 mLs 0.9% NaCl, 5% dextrose) IV continuous infusion

- Dosing range: 0.025 mg/hr – 0.3 mg/hr (0.5 -6 ml/hr)
 - Start at @ 2 mLs per hour
 - Titration by 1 mL (0.05 mg) or as clinically indicated per study investigator every 60 minutes for target RASS (0 to +1)
 - Maximum Rate: 6mLs/hr. (0.3 mg/hr.)
 - If RASS +2 to +3, decrease dose by 0.05mg (1 mL) or as clinically indicated per study investigator every 60 minutes or HOLD if at the lowest rate of 0.025 mg/hr (0.5ml/hr) and re-assess in 1 hour.
 - If RASS +4, HOLD regardless of rate and re-assess in 1 hour.
2. PI or co-investigator assessed patient response daily during the intervention phase (no longer than 72 hours).
- Daily interruption of infusion starting @ 0900 for 4 hours or until RASS of -1 to -2 .
 - A. Assess & document CAM-ICU and RASS BEFORE continuous infusion is interrupted
 - B. At the end of the interruption, assess patient’s RASS and CAM-ICU.
 - C. If patient regresses back to RASS -1 to -3 and CAM-ICU positive, then study infusion was restarted at the previous rate and re-assessed daily.
 - D. If daily interruption results in no change in RASS or CAM-ICU scores then study infusion was restarted @ the previous rate
 - Daily interruption occurred daily unless one of the following criteria were met resulting in discontinuation of study drug in the interim:
 - A. Primary attending caring for patient deemed discontinuation appropriate
 - a. Primary care team must *prospectively* notify the PI if the primary care team wishes to interrupt or discontinue the study infusion to provide clinical care to the patient.
 - B. RASS +2 to +4 while on infusion and agitation not controlled with standard treatments (i.e. anti-psychotics)
 - C. Rescue benzodiazepine needed due to signs of withdrawal according to the SHOT Scale
 - D. Remains CAM-ICU negative after interruption
 - E. ICU discharge (determined by physical transfer to lower level of care)
 - F. Adverse event attributable to study drug (i.e. supraventricular arrhythmia, seizure)
3. If episodic sedation was needed for a procedure (i.e. bronchoscopy)
- Study drug could be held (i.e. 30-60 minutes prior) and once the procedure was completed the study infusion could be restarted at previous rate.

As delineated above, the primary investigator and co-investigators were active participants in the study from pre-screening, enrollment, data collection, and data analysis. Relevant staff, including nursing personnel and medical staff, were utilized for coordination purposes.

Statistical Analysis

Baseline characteristics included age, sex, ICU service, Sequential Organ Failure Assessment (SOFA) score, Charlson Comorbidity Index, days in hospital prior to enrollment, time since last benzodiazepine administration, benzodiazepine indication, lorazepam equivalents (lorazepam 1 mg = midazolam 2 mg = diazepam 5 mg), home benzodiazepine use, and RASS prior to test dose. The original sample size calculation indicated that 40 patients in each group were required to detect a 30% difference (sd \pm 2 d) in delirium-free days, assuming p value less than 0.05 and 80% power. Descriptive statistics and the Wilcoxon rank-sum test were performed. The Kaplan–Meier method was used to characterize the probability of being delirium and coma free.

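### The only agitation endpoint leaves out episodes that settle when the infusion is lowered; add a descriptive by-arm count of any RASS +2 to +4, with episodes per infusion-day.

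*Combined protocol and SAP*

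**What the plan says.** Under Objectives, the primary safety outcome is "severe refractory agitation, which was defined as RASS of +2 to +4 that did not resolve by decreasing the infusion rate of study drug". The secondary outcomes are delirium resolution, ICU length of stay, "maximum rate and duration of study infusion, rescue sedative use, and mechanical ventilator-free days". None of them counts agitation episodes.

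Under Methods (Infusion titration post-randomization), the comparator is "standard of care + placebo (50 mLs 0.9% NaCl, 5% dextrose) IV continuous infusion". Both arms carry the same response to agitation: "If RASS +2 to +3, decrease dose by 0.05mg (1 mL) or as clinically indicated per study investigator every 60 minutes", with a hold if the patient is already at the lowest rate, and "If RASS +4, HOLD regardless of rate and re-assess in 1 hour". Both arms are titrated to RASS 0 to +1. The monitoring instruction is "Patient care order placed for nurse to monitor RASS every 1 hour". Response is assessed daily "during the intervention phase (no longer than 72 hours"), with "Daily interruption of infusion starting @ 0900 for 4 hours or until RASS of -1 to -2".

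The discontinuation criteria in the same section include agitation in this RASS range that standard treatments do not control (B), a patient who stays CAM-ICU negative once the infusion has been interrupted (D), and an adverse event attributed to study drug (F). These stop the infusion; they are not outcomes. Criterion B is also limited to agitation that failed to respond, and it judges response by a different test from the one under Objectives.

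The Statistical Analysis section mentions descriptive statistics in general terms and names no agitation measure.

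**The concern.** Whether an episode resolves on a rate decrease is known only after randomization, and the decrease means different things in the two arms. On flumazenil it reduces exposure to a drug that may be causing the agitation. On placebo it has no drug effect. The definition therefore tends to remove drug-induced, dose-responsive agitation, which a safety reader would want to see. A small between-arm difference in the refractory endpoint is compatible with a real excess of agitation on flumazenil.

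The titration target ends one RASS step below the +2 threshold, so overshoot is foreseeable. Maximum rate, infusion duration and rescue sedative use reflect such episodes only indirectly; an episode that settles on a lower rate may need no rescue drug. The documents do not claim that the endpoint measures agitation overall. The gap is that nothing listed does.

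**Working it through.** **Inputs.** From the documents: 40 patients per group (Statistical Analysis; calculated for delirium-free days, not for safety), at most 72 hours of intervention, and daily interruptions of up to 4 hours. The documents give no agitation figure to reproduce, so every rate below is assumed.

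**1. How much of an excess the endpoint counts**

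Let b = 0.10 be the background risk of any RASS +2 to +4 in both arms, and d = 0.15 the drug-induced risk among the remaining patients. Let r be the share of drug-induced episodes that settle on a rate decrease, and sp and sf the shares of background episodes that settle on placebo and on flumazenil.

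- Any agitation: placebo 0.100; flumazenil b + (1−b)d = 0.10 + 0.90 × 0.15 = 0.235. True difference +13.5 points, risk ratio 2.35.
- Counted on placebo: b(1−sp).
- Counted on flumazenil: b(1−sf) + (1−b)d(1−r).
- Counted difference: 0.135(1−r) − 0.10(sf−sp).

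| Background settling | r = 0.2 | r = 0.4 | r = 0.6 | r = 0.8 |
|---|---|---|---|---|
| Equal in both arms | +10.8 | +8.1 | +5.4 | +2.7 |
| 20% placebo, 50% flumazenil | +7.8 | – | +2.4 | −0.3 |
| 50% placebo, 20% flumazenil | +13.8 | – | +8.4 | +5.7 |

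Entries are percentage points. Example, second row at r = 0.6: flumazenil 0.050 + 0.135 × 0.4 = 0.104; placebo 0.10 × 0.8 = 0.080; difference 0.024.

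The risk ratio has no fixed direction either. At r = 0.6 the second row gives 0.104/0.080 = 1.30 and the third 0.134/0.050 = 2.68, against a true 2.35.

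A second illustration uses counts. Suppose 12/40 on flumazenil and 6/40 on placebo have any such episode. If 75% of these settle on flumazenil and 25% on placebo, the counted numbers are 12 × 0.25 = 3 and 6 × 0.75 = 4.5, so a two-fold excess changes direction. If 25% settle in both arms they are 9 and 4.5, and the ratio is preserved.

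**2. Why the added count needs a rate as well**

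Time on infusion can depend on response (criterion D). Constant rates that give 10% and 23.5% over three days are:

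- placebo: −ln(0.90)/3 = 0.035 per infusion-day;
- flumazenil: −ln(0.765)/3 = 0.089 per infusion-day; ratio 2.5.

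The flumazenil risk is then 1 − exp(−0.0893 × days):

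| Days on flumazenil | Flumazenil risk | Placebo risk over 3 days | Difference |
|---|---|---|---|
| 1 | 8.5% | 10% | −1.5 points |
| 2 | 16.4% | 10% | +6.4 points |
| 3 | 23.5% | 10% | +13.5 points |

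Unequal infusion time alone can hide a 2.5-fold rate ratio from a patient count.

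Interruptions can take 3 × 4 = 12 of 72 hours, one sixth, so the count must say whether they are included.

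**3. Precision at 40 per arm**

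- For example, 9/40 v 4/40: 22.5% − 10% = +12.5 points, exact unconditional 95% CI −4.3 to +29.9. A score interval is close, about −4.0 to +28.9.
- Power for 10% v 23.5%: about 36% by normal approximation, 28% by Fisher's exact test.

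**The case against.** The strongest reply is that this is an addition and not an error. A brief +2 that settles on a lower rate is a titration overshoot that the protocol already handles, and refractory agitation was presumably chosen to exclude it. The outcome list is introduced as what was included, so it may not be complete. Every rate above is assumed, the equal-settling row largely restates the definition, and the only reversal in the table needs an unexplained 50%/20% split in background settling together with r = 0.8.

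Much of this stands, and it is why the endpoint should be kept and the new count treated as descriptive. But nothing in the documents specifies a count of all episodes, and the central point does not need a reversal: it is enough that drug-induced agitation which settles is recorded nowhere as an outcome.

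The proposed measures also have limits. The patient count can mislead when infusion times differ. The per-day denominator includes holds, which agitation itself can trigger, and stopping can follow from agitation (criterion B). As worded below, the rate has no interval and makes no allowance for repeat episodes within a patient. Hence both figures should be shown together and neither should be tested.

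On data, the hourly order is printed under the flumazenil arm only, but both arms are titrated every 60 minutes to a RASS target under blinding, so readings should exist in both. The order is not described as study data collection, and abstraction could reach 80 × 72 = 5,760 readings. For interruptions, the text specifies assessments only before and at the end, so coverage there may be thinner. The document is in the past tense; if the data are already in hand, the table must be labelled as added afterwards, and the precision figures hold only if 40 per arm was reached.

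**Conclusion.** The concern holds, as a gap worth closing rather than an invalid endpoint. The listed outcomes allow a conclusion on refractory agitation but not on whether flumazenil raises RASS +2 to +4 agitation. Under the assumed 10% v 23.5%, with equal background settling, a true excess of 13.5 points would be counted as anything from +10.8 down to +2.7 as r goes from 0.2 to 0.8. With the arm-specific settling shown, the range is +13.8 to −0.3. These figures show what the definition can do; they do not predict this trial. That the endpoint omits episodes settled by a rate decrease, and that no listed outcome includes them, follows from the text alone.

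**What to change.** Keep the refractory endpoint and conclude only on refractory agitation from it. Add beside it, labelled descriptive:

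> Number of patients in each arm with any RASS of +2 to +4 from first start to final stop of study infusion (holds and daily interruptions included), whatever resolved it, as a risk difference (flumazenil minus placebo) with an exact 95% CI; and episodes per infusion-day by arm, where an episode is a run of consecutive RASS readings of +2 or more and infusion-days run from first start to final stop.

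As a clarification, reconcile the endpoint definition, which refers to decreasing the rate, with the titration section, which holds the infusion at RASS +4 or at the lowest rate. The plan should say whether an episode that resolves on a hold is classed as resolved or refractory. No treatment rule changes.

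The cost is one sentence, two table rows and the abstraction of RASS readings that are already ordered. The sample size and alpha are unaffected. The added count will include milder and self-settling episodes and agitation from other causes, such as benzodiazepine withdrawal, and it will be imprecise.

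### The primary safety endpoint can be met only during the infusion, so no stated outcome reports harm from the flumazenil test dose given to every enrolled subject, including non-responders who are never randomized

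*Combined protocol and SAP*

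**What the plan says.** **Endpoint (Objectives).** Severe refractory agitation is defined as "RASS of +2 to +4 that did not resolve by decreasing the infusion rate of study drug". The listed secondary outcomes are: "Secondary outcomes included probability of delirium resolution, ICU LOS, maximum rate and duration of study infusion, rescue sedative use, and mechanical ventilator-free days". None concerns adverse events, seizure, arrhythmia or the test dose.

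**Test dose (Methods, Test dose administration and monitoring).** Enrollment precedes dosing: "after consent was obtained enrollment into the trial occurred, subjects received a test dose of flumazenil". Each push is 0.1 to 0.5 mg, and "May repeat every 5-10 minutes up to a MAX of 2 mg total". For the study log, the stated entry is that "the PI entered each subject's test dose response (positive/negative) on a study log". A RASS change of +1 to +2 counts as response and leads to randomization; "patients that did not respond to test dose were not randomized".

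**Monitoring.** The same section and the lines that follow it provide for EKGs at 10 and 60 minutes after the first dose, filed in the subject's profile. Three staff roles stay at the bedside for 30 minutes after the last dose, and assessment runs up to 60 minutes after it.

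**Adverse events and analysis.** Seizure and supraventricular arrhythmia are named once, under Infusion titration post-randomization, as grounds for discontinuing study drug. The Statistical Analysis section names descriptive statistics, the Wilcoxon rank-sum test and Kaplan–Meier estimation. It defines no safety set.

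**The concern.** An event that happens before any infusion is running cannot fail to resolve when the infusion rate is lowered. The primary safety endpoint therefore excludes the test-dose stage by construction. At that stage the whole enrolled population, including future placebo patients, is exposed to active drug. For placebo patients and non-responders, the test dose is the only flumazenil that the trial gives them.

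If the plan is followed as written, an agitation episode, seizure or arrhythmia after the test dose could be seen, managed and charted without appearing in the trial's safety result. A reader would learn how the infusion was tolerated by patients selected for their reaction to the drug. The reader would learn nothing about what it took, in terms of harm, to select them.

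**Working it through.** The plan gives no figure for test-dose safety, so there is none to reproduce. Its 40 per group enters only as 2 × 40 = 80 randomized patients.

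**1. Which exposures can each outcome register?**

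| Group | Flumazenil received | Can meet the primary safety endpoint? |
|---|---|---|
| Responders, flumazenil arm | Test dose and infusion | During infusion only |
| Responders, placebo arm | Test dose only | During placebo infusion only |
| Non-responders | Test dose only | No |

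Among the secondary outcomes, only rescue sedative use could reflect test-dose agitation. It has no stated start time, and nothing extends it to subjects who were not randomized.

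**2. Size of the exposure.** Inputs are from the test-dose and infusion sections: pushes of 0.1 to 0.5 mg, total maximum 2 mg; infusion 0.025 to 0.3 mg/h, starting at 0.1 mg/h, for at most 72 h.

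- Full test dose in hours of infusion: 2 / 0.1 = 20 h at the starting rate; 2 / 0.3 = 6.7 h at the maximum rate.
- A single smallest push: 0.1 / 0.1 = 1 h at the starting rate.
- Cumulative infusion over 72 h, ignoring the daily interruptions: 0.025 × 72 = 1.8 mg at the lowest rate, 0.1 × 72 = 7.2 mg at the starting rate, 0.3 × 72 = 21.6 mg at the maximum.
- Relative to a full 2 mg test dose: 1.8 / 2 = 0.9, 7.2 / 2 = 3.6 and 21.6 / 2 = 10.8 times.

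The test dose is thus not trivial beside the infusion, but a long infusion can deliver several times more.

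**3. How many subjects are affected?** The response rate is not given, so the rates below are assumptions. Number dosed = 80 / response rate, rounded up; never randomized = dosed − 80.

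| Assumed response rate | Dosed | Never randomized |
|---|---|---|
| 90% | 89 | 9 |
| 80% | 100 | 20 |
| 70% | 115 | 35 |
| 50% | 160 | 80 |
| 30% | 267 | 187 |

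These are counts of exposed people, not of harms. If 5% of dosed subjects had a test-dose event (also an assumption), 89 × 0.05 = 4.5 to 160 × 0.05 = 8 events would be expected at response rates of 90% to 50%. Of these, 9 × 0.05 = 0.5 to 80 × 0.05 = 4 would fall in subjects never randomized.

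**4. Response rule against agitation range.** Eligible RASS is −3 to 0; response is a change of +1 to +2; the agitation range is +2 to +4.

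| RASS before | RASS after, if a response | Rise needed to reach +2 |
|---|---|---|
| −3 | −2, −1 | 5 |
| −2 | −1, 0 | 4 |
| −1 | 0, +1 | 3 |
| 0 | +1, +2 | 2 |

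From RASS 0, a change to +2 is a response and also lies in the agitation range. From any lower starting value, reaching +2 takes a rise of at least 3, which the response definition does not cover. Read literally, such a subject is not a responder and is not randomized, and the agitation enters no outcome.

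**The case against.** The stated hypothesis concerns the continuous infusion, and the test dose is an openly described step to select responders. Tying the primary safety endpoint to the randomized intervention is a legitimate choice in a pilot. The document is a short summary in the past tense: it speaks of a primary safety objective and says what secondary outcomes included, so neither list claims to be complete. Silence on adverse-event reporting is weak evidence that none took place. All of this stands. It limits the point to what the plan states, but it does not supply an outcome for test-dose harm in enrolled subjects.

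A reader might also infer stronger things that the documents do not support:

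- **That test-dose harm went unobserved or unrecorded.** It did not: bedside staff, RASS assessment and filed EKGs are all planned. Positive/negative response is merely the only item specified for the study log.
- **That the safety comparison is tilted towards flumazenil.** Both arms receive the test dose, so leaving out its events does not by itself favour either arm. Selecting patients whose RASS rises on the drug could even make infusion-phase agitation more likely.
- **That the test dose is about 27 times as intense as the infusion.** That figure takes four 0.5 mg pushes at 5-minute spacing (2 mg over 15 minutes = 8 mg/h; 8 / 0.3 = 26.7). It is an extreme corner of the permitted schedule and ignores cumulative dose.
- **That a known, large number of patients goes uncounted.** The counts above follow entirely from assumed response rates.

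**Conclusion.** The point holds as a gap in outcome definition and reporting. The primary safety endpoint covers the infusion phase in test-dose responders only, while all enrolled subjects receive flumazenil beforehand, and no stated outcome or analysis describes harm at that stage. It shows no error in the randomized comparison and changes no sample size.

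Its size can only be bounded. Per subject, the exposure is at most 2 mg, equal to 20 h at the starting rate or 6.7 h at the maximum rate, and may be much less. The number of subjects never randomized is unknown: 9 to 187 across assumed response rates of 90% to 30%. The gap in the primary safety endpoint applies to responders as well, so it would remain even if everyone responded. The overlap at RASS +2 and the unclassified rises above +2 follow from the plan's own definitions and rest on no assumption.

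**What to change.** - **Define a test-dose safety set**: all subjects given any test dose, randomized or not.
- **Report descriptively**, from first test dose to the end of the test-dose observation period: any RASS of +2 to +4, seizure, supraventricular arrhythmia on the planned EKGs, and rescue sedative use. Give counts with exact confidence intervals, split by responder status, with no arm comparison. State which period is meant, since the plan mentions both 30 and 60 minutes after the last dose.
- **Record the highest RASS and any complication on the existing test-dose log.** If the log is closed, take them from charted RASS and filed EKGs.
- **State the scope of the between-arm safety endpoint**: the infusion phase, in test-dose responders.
- **Reconcile the response rule with the agitation range**, so that a RASS of +2 after the test dose and a rise above +2 each have a defined status.

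The cost is two log items, or a chart extraction if the study has closed, and one table. More adverse events may be reported as a result. The safety-table changes alter no dose or clinical rule.

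### ICU length of stay has no rule for death, so in a raw comparison the arm with more ICU deaths can look better

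*Combined protocol and SAP*

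**What the plan says.** ICU LOS is named once, in Objectives, in the list of secondary outcomes: "Secondary outcomes included probability of delirium resolution, ICU LOS, maximum rate and duration of study infusion". No section gives its starting point, its end, or how a patient who dies in the ICU is counted.

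Other parts of the plan bear on this:

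- **Primary endpoint (Objectives).** Delirium-free days are "the number of days in the first 14 days during which the patient was alive without delirium or coma from any cause". Death earns no credit here.
- **Rest of the secondary list (Objectives).** It ends with "rescue sedative use, and mechanical ventilator-free days". Ventilation is thus named in a free-days form, though without a definition. Mortality is not listed as an outcome.
- **Methods (Statistical Analysis).** "Descriptive statistics and the Wilcoxon rank-sum test were performed". Neither is tied to a named outcome. Kaplan–Meier has one stated use: "The Kaplan–Meier method was used to characterize the probability of being delirium and coma free".
- **Time before enrollment.** The screening text waives a new urine drug screen in certain cases where "the patient was greater than 72 hrs from admission". Statistical Analysis lists "days in hospital prior to enrollment" as a baseline variable.
- **ICU discharge.** The criteria for stopping study drug define it by physical move to a lower level of care. The plan does not carry that definition over to LOS.

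**The concern.** A short ICU stay can mean early recovery or early death. Raw LOS does not separate them. A patient who dies in the ICU on day 3 has a shorter stay than one discharged alive on day 9, and a rank-sum comparison puts the death on the favourable side. The patients are critically ill, so some deaths before discharge are foreseeable. With 40 per group, the arms could differ in deaths by chance alone.

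Because mortality is not a listed outcome, the plan does not require a comparison of deaths beside LOS that would show a reader what had happened. A shorter stay on flumazenil could be reported as faster recovery when it reflects more deaths. The reverse also holds: fewer deaths on flumazenil could make its stay look longer.

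The unstated start is a smaller, separate matter. If LOS runs from ICU admission, it includes days that the study drug cannot influence.

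**Working it through.** **1. Is there a figure in the plan to reproduce?** Not for ICU LOS. The only design figure, 40 per group, concerns delirium-free days and is used below only as the trial size.

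**2. Inputs.** The documents give no ICU mortality or LOS distribution, so all of these are assumptions:

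- Survivor LOS S: log-normal, median 9 days, log-SD 0.6, identical in both arms.
- Time of ICU death D: uniform over days 1 to 10, mean 5.5.
- Proportion p dying in the ICU: 12% in one arm and 23% in the other, then 15% and 31%.
- Time is counted from randomization.

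**3. Mean LOS.** The survivor mean is 9 × exp(0.6²/2) = 10.77 days. The arm mean is (1 − p) × 10.77 + p × 5.5.

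- 12%: 0.88 × 10.77 + 0.12 × 5.5 = 10.14
- 23%: 0.77 × 10.77 + 0.23 × 5.5 = 9.56
- Gap: 0.11 × (10.77 − 5.5) = 0.58 day, in favour of the arm with more deaths
- At 15% vs 31%: 0.16 × 5.27 = 0.84 day

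**4. Median LOS.** Solve (1 − p) × Φ[(ln x − ln 9)/0.6] + p × (x − 1)/9 = 0.5. This gives 8.42 days at 12% and 7.96 at 23%, a gap of 0.46 day.

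**5. What the rank-sum test sees.** Let q be the chance that a death time is shorter than a survivor's stay, that is, P(S > u) averaged over u from 1 to 10. Here q = 0.769. The chance that a patient from the arm with more deaths has the shorter stay is 0.5 + (p₂ − p₁)(q − 0.5) = 0.5 + 0.11 × 0.269 = 0.53. No effect would be 0.50. In simulated trials of 40 per arm, a two-sided rank-sum p<0.05 in favour of that arm occurs in about 6.5% of trials, against 2.5% expected.

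**6. ICU-free days to day 14, same inputs.** A survivor's expected value is E[max(14 − S, 0)] = 4.80, and a death scores 0.

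- 12%: 0.88 × 4.80 = 4.2
- 23%: 0.77 × 4.80 = 3.7

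The arm with more deaths now has the worse result.

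**7. A second set of assumptions, and the start of LOS.** Time to live discharge is log-normal with median 8 days and log-SD 0.8 in both arms. Death is uniform over the stay, ICU time before randomization has median 5 days (log-SD 0.7), and there are 40 patients per arm.

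| Deaths (arm 1 vs arm 2) | LOS from | Median LOS, arm 1 vs arm 2 | p<0.05 favouring arm 2 |
|---|---|---|---|
| 20% vs 20% | randomization | 7.0 vs 7.0 | 2.4% |
| 20% vs 20% | ICU admission | 13.5 vs 13.5 | 2.6% |
| 20% vs 40% | randomization | 7.0 vs 6.0 | 11.4% |
| 20% vs 40% | ICU admission | 13.5 vs 12.5 | 7.8% |

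The bias comes from death alone. With equal deaths, days before randomization create no advantage. With unequal deaths they dilute the false signal. Ranking deaths as the worst outcome cuts the favourable p<0.05 rate to 0.3% or less in every scenario tried with unequal deaths.

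**The case against.** The best counter-argument is that little follows from this. ICU LOS is one of several secondary outcomes in a pilot, and the primary endpoint already requires the patient to be alive. The infusion lasts at most 72 hours, and nothing in the documents predicts a difference in mortality, so a near-doubling of deaths is purely assumed. Even then the shift is about half a day. The plan does not assign the rank-sum test to LOS, which may only have been described. Reporting ICU deaths next to LOS would also expose the problem.

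Most of this stands and limits the weight of the point. It does not remove it. A table of LOS by arm invites the same misreading without a test, and the plan calls for no report of deaths beside it.

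A reader might also infer more than the documents support:

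- **That days before randomization help the arm with more deaths.** They do not. They are balanced in expectation and only add noise.
- **That the plan expects enrollment after 72 hours.** The text saying that if "the patient was greater than 72 hrs from admission there was no requirement for ordering one" is a conditional waiver of a drug screen. It allows for such patients, and it does not say that the admission meant is ICU admission. The baseline variable counts hospital days, not ICU days.
- **That LOS is defined from ICU admission.** The start is simply not stated.

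**Conclusion.** The concern holds for the missing death rule. As named, ICU LOS treats an ICU death as a short stay, and a raw comparison can favour the arm with more deaths. On the assumed inputs the distortion is modest: about 0.6 day in the mean and 0.5 day in the median at 12% vs 23% deaths, with a rank-sum probability of 0.53, and about 0.8 day in the mean at 15% vs 31%. The direction needs only that deaths tend to come earlier than live discharges. The size depends entirely on mortality and LOS values that the documents do not give.

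It would be too strong to say that LOS can tell us nothing about ICU recovery, since with balanced deaths it is interpretable. Nor do the documents suggest that flumazenil raises mortality. The undefined start is a separate gap that costs precision and does not bias the comparison. The primary endpoint is unaffected. This change should be made, but the trial's main conclusion does not turn on it.

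**What to change.** In Objectives and in Statistical Analysis, make the between-arm outcome ICU-free days from randomization to day 14: days alive and out of the ICU, with death by day 14 scored 0. This matches the primary endpoint's 14-day length and its refusal to credit death. Name the rank-sum test for it. Keep ICU LOS, counted from randomization, as a description shown separately for survivors and for patients who died, with the number of ICU deaths per arm.

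The cost is about one sentence in each section and little or no new data. The primary endpoint already needs vital status to day 14, and the plan has a working definition of ICU discharge. The change can be made at the analysis stage. If LOS results by arm have already been seen, the report should say so.

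The downside is small: every stay beyond day 14 scores 0, the same as a death. Under the first set of assumptions that is 1 − Φ[ln(14/9)/0.6] = 1 − Φ(0.736), or about 23% of survivors. The descriptive LOS table keeps that information.
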